3.2 Registration Inclusion Criteria

- 3.2.1 For phase 2 only:

- 3.2.1.1 Patient has measurable disease per RECIST 1.1 for non-pleural disease or modified RECIST 1.1 (mRECIST) for pleural disease.

Note: For pleural disease, this is defined as at least one lesion that can be accurately measured perpendicular to the chest wall or mediastinum that is ≥ 10 mm (≥ 1 cm). For extra pleural disease, measurable disease is defined as at least one lesion that can be accurately measured in at least one dimension (longest diameter to be recorded for non-nodal lesions and short axis for nodal lesions) as ≥ 10 mm (≥ 1 cm) for non-nodal lesions and ≥ 15 mm (≥ 1.5 cm) for nodal lesions with spiral CT scan, MRI, or calipers by clinical exam as per RECIST 1.1.

- 3.2.1.2 Tissue submitted for testing at pre-registration shows moderate or stronger mesothelin expression in $\geq 30\%$ of the tumor cells.

3.2.2 For phase 1 and phase 2:

3.2.2.1 Patients must have received platinum-based therapy with or without bevacizumab.

3.2.2.2 Age \geq 18 years.

Note: Because MPM primarily affects older adults and no dosing or adverse event data are currently available on the use of anetumab ravidansine and pembrolizumab in patients $<$ 18 years of age, children are excluded from this study, but will be eligible for future pediatric trials.

3.2.2.3 ECOG performance status $<$ 2 (Karnofsky \geq 70%, see Appendix A).

3.2.2.4 Patients must have normal organ and marrow function as defined below:

• Leukocytes	\geq 3,000/mcL
• Absolute neutrophil count	\geq 1,500/mcL
• Platelets	\geq 100,000/mcL
• Total bilirubin	Within normal institutional limits
• AST (SGOT) AND ALT (SGPT)	\leq 2.5 \times institutional upper limit of normal (ULN)
• Creatinine	Within normal institutional limits
OR	
Creatinine clearance	\geq 60 mL/min/1.73 m ² for patients with creatinine levels above institutional normal.

3.2.2.5 International normalized ratio (INR) or prothrombin time (PT) \leq 1.5 \times ULN AND partial thromboplastin time (PTT) or activated PTT (aPTT) \leq 1.5 \times ULN, unless patient is on stable dose of anti-coagulation therapy in which case patients will be allowed to participate if they have no signs of bleeding or clotting and the INR/PT and PTT/aPTT results are compatible with an acceptable risk-benefit ratio as per the Investigator's discretion.

3.2.2.6 Negative serum pregnancy test for females of child bearing potential.

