Note: Females are considered to **not** be of child bearing potential if any of the following apply:

- Postmenopausal (defined as at least 12 months with no menses without an alternative medical cause; in women < 45 years of age, a high follicle stimulating hormone (FSH) level in the postmenopausal range may be used to confirm a postmenopausal state in women not using hormonal contraception or hormonal replacement therapy. In the absence of 12 months of amenorrhea, a single FSH measurement is insufficient.);
- Have had a hysterectomy and/or bilateral oophorectomy, bilateral salpingectomy or bilateral tubal ligation/occlusion, at least 6 weeks prior to screening;
- Has a congenital or acquired condition that prevents childbearing.

3.2.2.7 Patient agrees to use one of the following acceptable methods of contraception prior to study entry, during study participation, and for at least six months after receiving the last dose of study treatment:

Acceptable methods of contraception are:

Single method (1 of the following is acceptable):

- Abstinence, if consistently employed as the patient's preferred and usual lifestyle and if considered acceptable by local regulatory agencies and Institutional Review Boards (IRBs)
- intrauterine device (IUD)
- vasectomy of a female patient's male partner
- contraceptive rod implanted into the skin

Combination method (requires use of 2 of the following):

- diaphragm with spermicide (cannot be used in conjunction with cervical cap/spermicide)
- cervical cap with spermicide (nulliparous women only)
- contraceptive sponge (nulliparous women only)
- male condom or female condom (cannot be used together)
- hormonal contraceptive: oral contraceptive pill (estrogen/progestin pill or progestin-only pill), contraceptive skin patch, vaginal contraceptive ring, or subcutaneous contraceptive injection

3.2.2.8 Ability to understand and the willingness to sign a written informed consent document, unless patient is of impaired decision making capacity in which case patient may be eligible if they have a Legal Authorized representative or caretaker available.

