- Radiation therapy (Note: Radiation therapy to a symptomatic solitary lesion or to the brain may be considered on an exceptional case by case basis after consultation with CTEP. The patient must have clear measurable disease outside the radiated field. Administration of palliative radiation therapy will be considered clinical progression for the purposes of determining PFS.)
- Live vaccines within 30 days prior to the first dose of trial treatment and while participating in the trial. Examples of live vaccines include, but are not limited to, the following: measles, mumps, rubella, chicken pox, yellow fever, rabies,

Bacillus Chalmette–Guérin (BCG), and typhoid (oral) vaccine. Seasonal influenza vaccines for injection are generally killed virus vaccines and are allowed; however, intranasal influenza vaccines (e.g., Flu-Mist®) are live attenuated vaccines, and are not allowed.

- Systemic glucocorticoids for any purpose other than to modulate symptoms from an event of suspected immunologic etiology. The use of physiologic doses of corticosteroids may be approved after consultation with the study PI and CTEP.

3.3.8 Uncontrolled intercurrent illness including, but not limited to, ongoing or active infection, symptomatic congestive heart failure, unstable angina pectoris, cardiac arrhythmia, or psychiatric illness/social situations that would limit compliance with study requirements.

3.3.9 Women who are pregnant or breastfeeding.

Note: Pregnant women are excluded from this study because anetumab ravidansine and pembrolizumab are agents with the potential for teratogenic or abortifacient effects. Because there is an unknown but potential risk for adverse events in nursing infants secondary to treatment of the mother with anetumab ravidansine and pembrolizumab, breastfeeding should be discontinued if the mother is treated with anetumab ravidansine or pembrolizumab.

3.3.10 HIV-positive patients who do not meet all of the following and/or are on HIV medications considered to be strong inhibitors or inducers of CYP3A4:

- Undetectable HIV viral load by standard clinical assay within 6 months of registration
- Willing to adhere to antiretroviral therapy that has minimal overlapping toxicity or pharmacokinetic interactions with protocol therapy
- No AIDS-defining events other within the past 12 months
- Near normal life expectancy if not for the presence of the cancer

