4.4 General Guidelines

Following registration, patients should begin protocol treatment within 14 days. Issues that would cause treatment delays should be discussed with the Principal Investigator. If a patient does not receive protocol therapy following registration, the patient's registration on the study may be canceled. The Study Coordinator should be notified of cancellations as soon as possible.

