10. STUDY CALENDAR

Tumor tissue for the mesothelin expression assay is mandatory at pre-registration to establish eligibility for Phase 2 subjects. Pre-study evaluations are to be conducted within 14 days of registration unless stated otherwise. An ophthalmological exam is to be conducted within 28 days prior to the start of protocol therapy. Scans and x-rays must be done < 4 weeks prior to the start of therapy. Windows of \pm 1 to 2 days are permissible for cycles 1, 2 and 3; windows of \pm 3 days are permissible for cycles 4 and beyond. In the event that the patient's condition is deteriorating, laboratory evaluations should be repeated within 48 hours prior to initiation of the next cycle of therapy.

	Pre-registration (Phase 2 only)	Pre-study	Cycle 1			Cycle 2			Cycle 3			Cycle 4 and higher			Off Study ^k
			Wk 1	Wk 2	Wk 3	Wk 4	Wk 5	Wk 6	Wk 7	Wk 8	Wk 9	Wk 10	Wk 11	Wk 12	
Anetumab raptansine			A			A			A			A			
Pembrolizumab			B			B			B			B			
Informed consent		X													
Concurrent meds		X	X-----X												
Physical exam ^a		X	X			X			X			X			X
Ophthalmologic exam ^b		X				X			X			X			
Performance status		X	X			X			X			X			X
CBC w/diff, plts		X	X	X	X	X	X	X	X	X	X	X			X
Serum chemistry ^c		X	X	X	X	X	X	X	X	X	X	X			X
TSH, T3, T4 ^d		X	X			X			X			X			X
PT/INR, aPTT		X													
Serum pregnancy ^e		X													
ECG		X				X			X			X			

	Pre-registration (Phase 2 only)	Pre-study	Cycle 1			Cycle 2			Cycle 3			Cycle 4 and higher			Off Study ^k
			Wk 1	Wk 2	Wk 3	Wk 4	Wk 5	Wk 6	Wk 7	Wk 8	Wk 9	Wk 10	Wk 11	Wk 12	
Echo or MUGA ^f		X													
Adverse event evaluation			X-----												X
Radiologic evaluation/ Tumor measurements		X	Radiologic evaluation and tumor measurements are performed at the end of cycle 3/before cycle 4 begins and every 3 cycles thereafter. Documentation (radiologic) must be provided for patients removed from study for progressive disease.												X
Tissue for mesothelin assay ^g	X	X													
Tissue for PD-L1 assay ^h		X													
Blood for PKs and correlative studies ⁱ		X	X	X		X			X	X		X			
PRO-CTCAE ^j			X	X	X	X	X	X	X	X	X				X

A: Anetumab Ravtansine: ***For all phase 1 and phase 2 group 2 patients:*** Dose as determined by the phase 1 study by IV infusion over 60 minutes on day 1 of each cycle for up to 12 months total. Anetumab ravidansine is to be administered prior to pembrolizumab.

B: Pembrolizumab: 200 mg by IV infusion over 30 minutes on day 1 of each cycle for up to 24 months total for all groups.

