- a: Physical exam at pre-study includes height/weight, vital signs, demographics and medical history. Physical exam at all other visits includes weight and vital signs. Vital signs include pulse, blood pressure and temperature.
- b: For all patients at screening then only those randomized to receive anetumab ravidansine: Perform ophthalmologic exam within 28 days prior to Cycle 1 Day 1. The exam will include visual acuity [BCVA according to ETDRS, or Snellen, or Landolt C or other charts], intra-ocular pressure, dry eye test [Schirmer test] and slit lamp. For all subsequent cycles after Cycle 1, visual acuity and a slit lamp examination will be repeated before infusion in every cycle and at safety follow-up visit, or more frequently at investigator's and ophthalmologist's discretion. The IOP measurement is to be repeated during anetumab ravidansine therapy if the

patient receives steroid eye drops for more than 10 days as treatment for corneal epitheliopathy. This measurement is performed at 2 weeks and 6 weeks after the initiation of steroid treatment. If IOP increases by < 7 mmHg, the frequency of IOP evaluation can be reduced to every 4 months. If IOP increases by ≥ 7 mmHg, a medical management plan with follow-up IOP evaluations will be initiated after consultation with an ophthalmologist and investigator. The Schirmer test is performed at baseline and then at C3D1 and C5D1. All these tests may be repeated during treatment at the investigator's discretion.

Note: Ophthalmologic exams do not need to be continued for patients assigned to combination therapy who later discontinue anetumab ravidansine due to non-ocular toxicities.

- c: Labs include albumin, alkaline phosphatase, total bilirubin, bicarbonate, BUN, calcium, chloride, creatinine, glucose, LDH, phosphorus, potassium, total protein, SGOT [AST], SGPT [ALT], sodium.
- d: Patients receiving pembrolizumab should be monitored for changes in thyroid function at the timepoints listed in the calendar and as clinically indicated for clinical signs and symptoms of thyroid disorders.
- e: Serum pregnancy test for females of childbearing potential.
- f: Echocardiogram or Multigated Acquisition Scan (MUGA; radionuclide angiography) is performed at pre-study and then only as clinically indicated.

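### The only scheduled pregnancy test is tied to registration and not repeated before the first dose, so it can be 19 to 28 days old at dosing

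*Combined protocol and SAP*

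**What the plan says.** Section 10 marks the serum pregnancy test in the pre-study column only. There is no mark in Cycle 1, in later cycles or at off-study. Footnote e says who is tested and nothing about when: "Serum pregnancy test for females of childbearing potential". The eligibility criterion, 3.2.2.6, is equally silent on the age of the test: "Negative serum pregnancy test for females of child bearing potential". The calendar's default window therefore applies: "Pre-study evaluations are to be conducted within 14 days of registration unless stated otherwise".

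Section 4.4 sets the next interval: "Following registration, patients should begin protocol treatment within 14 days". That is a recommendation, and delays are to be discussed with the Principal Investigator. Section 5.1.2 allows pembrolizumab to be given up to 3 days either side of the scheduled Day 1 and adds, in parentheses, an allowance of up to 5 days after randomization.

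Section 3.3.9 gives the reason for excluding pregnant women: anetumab ravtansine and pembrolizumab are "agents with the potential for teratogenic or abortifacient effects".

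**The concern.** The exclusion exists to keep a pregnant woman from being dosed, yet the test that enforces it is timed to registration and never repeated. A negative result describes the day of the blood draw. Conception shortly before or after that day would not show, and nothing in the schedule would detect it before the first infusion.

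What is at stake is avoidable fetal exposure to an antibody-drug conjugate and a PD-1 antibody. It is a participant-safety matter and has no bearing on the efficacy comparison.

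**Working it through.** The plan states no figure for the age of the test at first dose, so there is nothing to reproduce. The age follows from adding the permitted intervals.

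**Oldest permitted test at first dose**

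- Test to registration: up to 14 days (Section 10). The test comes before registration, because Section 4.3.1 has sites verify eligibility before they register a patient.
- Registration to first dose: up to 14 days (Section 4.4).
- Main reading: 14 + 14 = 28 days, and longer if a delay is agreed.
- Alternative for phase 2: read the 5 days in Section 5.1.2 as a cap and assume same-day registration and randomization. Then 14 + 5 = 19 days.

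**Does anything else close the gap?**

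- The 48-hour laboratory repeat in Section 10 applies only to a patient whose condition is deteriorating.
- The chemistry panel in footnote c, drawn again at Cycle 1 Week 1, contains no pregnancy test.
- Contraception is required: 3.2.2.7 asks for "acceptable methods of contraception prior to study entry, during study participation" and for at least six months after the last dose. Section 5.5 asks women to report a suspected pregnancy, and Section 7.7 removes a patient who becomes pregnant on pembrolizumab. These lower the risk, but none verifies status on the day of dosing.

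**How many women are concerned**

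- Women in the planned enrollment table (13.3.3): (42 + 11)/134 = 53/134 = 39.6%.
- Applied to the phase 2 maximum of 110 (13.3.1): 0.3955 × 110 = 43.5, about 44 women.
- The documents do not give the share of childbearing potential. Section 3.2.2.2 points to a low one ("Because MPM primarily affects older adults"). Assumed range 2% to 10%: 43.5 × 0.02 = 0.87 and 43.5 × 0.10 = 4.35, so about 1 to 4 women.

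**Expected pregnancies in the gap**

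Formula: women × yearly contraceptive failure × days/365. The failure rate is assumed to be 1% to 10%, and every such woman is assumed to wait the full interval.

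| Gap | Low | High |
|---|---|---|
| 19 days | 0.87 × 0.01 × 19/365 = 0.0005 | 4.35 × 0.10 × 19/365 = 0.023 |
| 28 days | 0.87 × 0.01 × 28/365 = 0.0007 | 4.35 × 0.10 × 28/365 = 0.033 |

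**The case against.** The strongest reply has four parts.

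1. **The 28 days is not the only reading.** Both phase 2 groups receive pembrolizumab, so the Section 5.1.2 parenthetical could limit the start to 5 days after randomization, giving 19 days. This stands as an alternative. The sentence concerns administrative flexibility and does not clearly override Section 4.4, so the age is best given as 19 to 28 days. On either reading no repeat is required.
2. **A screening test of about four weeks is normal in this protocol.** The calendar says: "An ophthalmological exam is to be conducted within 28 days prior to the start of protocol therapy". Scans may be almost as old, and PT/INR is also done once at pre-study. This stands too. A reader might infer that the protocol holds other screening tests to a shorter window, but the eye exam has the same 28 days. What differs is the anchor: that exam is tied to the start of therapy and the pregnancy test is tied to registration.
3. **The larger exposure comes later.** Pembrolizumab may run 24 months with no pregnancy test in any cycle. At a constant failure rate, that is 730/28 = about 26 times the pre-dose gap for a woman treated that long. The arithmetic is right, and the change below does not address that period. It does not remove the reason to check before the first dose.
4. **The benefit is tiny and 72 hours is a preference.** Both are true, and they determine the rating.

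**Conclusion.** The gap is real and minor. A site that follows the plan can give the first dose on a pregnancy test up to 28 days old under Section 4.4, or up to 19 days old in phase 2 under the alternative reading of Section 5.1.2.

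Two stronger inferences are not supported. First, 39.6% is the planned share of women, not the share who would be tested. Only women of childbearing potential are tested, about 1 to 4 in phase 2 if they make up 2% to 10% of the women. Second, the gap does not make an exposed pregnancy likely. Expected numbers are 0.0005 to 0.023 over 19 days and 0.0007 to 0.033 over 28 days, well below one. The upper ends need 10% childbearing potential, 10% yearly failure and the full wait for every woman.

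The response rate, its denominator and power are unaffected. The case for change is that the possible harm is irreversible and the check is cheap.

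**What to change.** Amend the serum pregnancy row and footnote e of the Section 10 calendar, for both phase 2 groups (phase 1 accrual is already reported as complete in Section 2.3.2.2). Suggested content:

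- Women of childbearing potential must have a negative serum pregnancy test within 72 hours before dosing on Cycle 1 Day 1.
- Repeat the test only if the pre-study test is older than that, using blood already drawn for CBC and chemistry.
- The result must be known before either agent is given.
- Keep the pre-study test for eligibility.

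This reduces the maximum age to 3 days: 28 − 3 = 25 days less on the main reading, 19 − 3 = 16 days less on the alternative. The cost is at most one extra assay for each woman of childbearing potential and a possible wait for the result before infusion. No other section needs to change.

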ClinicalTrials.gov identifier: NCT03126630

NCI-Supplied Agent(s):

Anetumab ravidansine (NSC 791065)
Pembrolizumab (MK-3475) (NSC 776864)

IND Sponsor: DCTD, NCI.

Protocol Type / Version # / Version Date:

Original/ Version 1 / March 9, 2017
Resubmission / Version 2 / April 29, 2017
Resubmission / Version 3 / June 13, 2017
Resubmission / Version 4 / July 14, 2017
Resubmission / Version 5 / July 28, 2017
Resubmission / Version 6 / October 10, 2017
Resubmission / Version 7 / December 13, 2017
Resubmission / Version 8 / December 29, 2017
Amendment 1 / Version 9 / May 10, 2018
Amendment 2 / Version 10 / June 28, 2018
Amendment 3 / Version 11 / July 20, 2018
Amendment 4 / Version 12 / December 3, 2018
Amendment 5 / Version 13 / December 26, 2018
Amendment 6 / Version 14 / February 15, 2019
Amendment 7 / Version 15 / May 16, 2019
Amendment 7 / Version 16 / July 1, 2019
Amendment 8 / Version 17 / October 2, 2019
Amendment 9 / Version 18 / November 25, 2019
Amendment 10 / Version 19 / January 21, 2020
Amendment 10 / Version 20 / January 31, 2020
Amendment 11 / Version 21 / February 24, 2020
Amendment 12 / Version 22 / July 28, 2020
Amendment 13 / Version 23 / September 25, 2020
Amendment 14 / Version 24 / December 15, 2020
Amendment 15 / Version 25 / May 3, 2021

NCI Protocol #: 10107

[figure not shown]
Local Protocol #: MC1721

NCI Version Date: October 25, 2021

3

[figure not shown]
Amendment 16 / Version 26 / October 25, 2021

SCHEMA – Phase 1 Study

1. Cycle length = 21 days
2. Anetumab ravidansine is to be administered prior to pembrolizumab (MK-3475) when given in combination

SCHEMA – Randomized Phase 2 Study

1. Mesothelin expression may be determined while a patient is receiving frontline therapy and registration may occur at time of progression. Submitted tissue must show moderate or stronger mesothelin expression in $\geq 30\%$ of the tumor cells for the patient to be eligible for and registered to the study. Submit slides or a tissue block to the central laboratory for the mesothelin expression assay as per Section 9.2.1.
2. Cycle length = 21 days
3. Anetumab rrvtansine is to be administered prior to pembrolizumab when given in combination

TABLE OF CONTENTS

SCHEMA – Phase 1 Study	4
SCHEMA – Randomized Phase 2 Study	5
1. OBJECTIVES	8
1.1 Primary Objectives.....	8
1.2 Secondary Objectives.....	8
1.3 Correlative Study Objectives	8
2. BACKGROUND	9
2.1 Malignant Pleural Mesothelioma.....	9
2.2 CTEP IND Agents	9
2.3 Rationale	12

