5.5 Duration of Therapy

In the absence of treatment delays due to adverse event(s), treatment with anetumab ravtansine may continue for up to a maximum of 12 months and treatment with pembrolizumab (all groups) may continue for up to 24 months or until one of the following criteria applies:

- Disease progression; see sections 5.7 and 5.9.
- Intercurrent illness that prevents further administration of treatment
- Adverse event(s) which require(s) treatment discontinuation:
 - Any dosing interruption lasting >12 weeks with the following exceptions:
Dosing interruptions >12 weeks that occur for non-drug-related reasons may be allowed if approved by the Principal Investigator. Prior to re-initiating treatment in a patient with a dosing interruption lasting >12 weeks, the Principal Investigator must be consulted.
 - Tumor assessments should continue as per protocol even if dosing is interrupted.
- Patient decides to withdraw from the study
- General or specific changes in the patient's condition render the patient unacceptable for further treatment in the judgment of the investigator
- Clinical progression is defined as occurring when a patient's condition has deteriorated and the patient cannot continue with study treatment per the investigator's judgment regardless of imaging findings
- Patient non-compliance
- Pregnancy
 - All women of child bearing potential should be instructed to contact the investigator immediately if they suspect they might be pregnant (e.g., missed or late menstrual period) at any time during study participation.
 - The investigator must immediately notify CTEP in the event of a confirmed pregnancy in a patient participating in the study.
- Termination of the study by sponsor
- The drug manufacturer can no longer provide the study agent
- If a patient has had a confirmed complete response (CR) that have been treated for at least 24 weeks with pembrolizumab and has continued at least two cycles beyond complete response, discussion between the treating physician and investigator regarding discontinuation of study treatment may be considered.

The reason(s) for protocol therapy discontinuation must be documented in the Case Report Form (CRF).

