6.2 Dose Modifications for Anetumab Ravtansine

Dose Level	Anetumab Ravtansine Dose
1	6.5 mg/kg
-1	5.5 mg/kg
-2	4.5 mg/kg

Neutrophil count decreased ^{1, 2}	Management/Next Dose
\leq Grade 1	No change in dose
Grade 2	No change in dose
Grade 3	Hold ² until $<$ Grade 2. Resume at one dose level lower.
Grade 4	Hold ² until $<$ Grade 2. Resume at one dose level lower.
1.	Patients with febrile neutropenia should hold ^{**} until $<$ grade 2 and resume at one dose level lower.
2.	G-CSF and other hematopoietic growth factors may be used during the study in the management of acute toxicity such as febrile neutropenia when clinically indicated per ASCO Recommendations for Therapeutic Use of CSF (63) or at the discretion of the investigator; however they may not be substituted for a required dose reduction.
3.	Patients requiring a delay of $>$ 12 weeks should go off protocol therapy.

Platelet count decreased¹	Management/Next Dose
≤ Grade 1	No change in dose
Grade 2	No change in dose
Grade 3	Hold ² until < Grade 2. Resume at one dose level lower.
Grade 4	Hold ² until < Grade 2. Resume at one dose level lower.
1.	Patients with active bleeding related to drug-induced thrombocytopenia should reduce by one dose level.
2.	Patients requiring a delay of > 12 weeks should go off protocol therapy.

Non-hematologic toxicities	Management/Next Dose
≤ Grade 1	No change in dose.
Grade 2	No change in dose.
Grade 3	Hold ¹ until ≤ Grade 2. Resume at same level or at one dose level lower, per investigator's discretion. ²
Grade 4	Off protocol therapy
1.	Patients requiring a delay of > 12 weeks should go off protocol therapy.
2.	Patients requiring > two dose reductions should go off protocol therapy.

Corneal Epitheliopathy	Definition	Management/Next Dose^{1, 2}
Grade 0	No pathologic changes	No change in anetumab ravtansine; ocular lubricants at discretion of investigator or ophthalmologist
Grade 1	Any stage of superficial punctate keratitis (SPK; as per the Oxford Schema for grading SPK from stage 0 to IV)	No change in anetumab ravtansine; ocular lubricants; add topical steroids if SPK shows treatment emergent progression by ≥ 2 SPK grades

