6.4 Continuation of Therapy When One Agent is Held or Discontinued

Patients who participate in the Phase 1 portion of this trial or are assigned to Treatment Group 2 (the combination of anetumab ravidansine and pembrolizumab) may continue to receive one agent if the other is held or discontinued for toxicity, and the toxicity is clearly attributable to the held or discontinued agent. If the toxicity in question is possibly related to either agent, then both agents should be held. These decisions may be discussed with the Principal Investigator.

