11.1.1 Schedule of Evaluations

For the purposes of this study, patients should be re-evaluated for response every 9 weeks. In addition to a baseline scan, confirmatory scans should also be obtained 4-6 weeks following initial documentation of objective response.

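### The study calendar times scans by treatment cycle and Section 11.1.1 times them every 9 weeks; if sites follow the calendar, unequal dose delays could bias PFS, a secondary endpoint, towards the combination arm

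*Combined protocol and SAP*

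**What the plan says.** Two places set the imaging schedule.

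- Section 10, study calendar, tumor measurement row: "Radiologic evaluation and tumor measurements are performed at the end of cycle 3/before cycle 4 begins and every 3 cycles thereafter".
- Section 11.1.1: "For the purposes of this study, patients should be re-evaluated for response every 9 weeks". It gives no starting point for the count and does not mention delayed cycles.

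These provisions decide whether the two can differ:

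- The schema gives "Cycle length = 21 days".
- Section 5.8 lets treatment resume late, within a 12-week delay period. Section 6.2 takes patients off therapy only after a longer delay.
- Section 5.5 adds "Tumor assessments should continue as per protocol even if dosing is interrupted". The line stands under the bullet on interruptions longer than 12 weeks and does not name a schedule.
- Under Section 6.4, patients on the combination "may continue to receive one agent if the other is held or discontinued for toxicity", provided the toxicity is clearly due to the held agent. Otherwise: "If the toxicity in question is possibly related to either agent, then both agents should be held".

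Sections 11.1.7 and 13.5.3 count PFS from start of treatment to the first documented progression or death, and compare the arms by log-rank test. Section 13.5.3 states no significance level, sidedness or number of events. Section 11.1.8 leaves the reading of scans to the local investigator.

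**The concern.** Progression is dated at the scan that shows it, so the scan interval is part of the PFS measurement. A site working from the calendar row would scan before cycle 4 whenever cycle 4 happens to start, and would be compliant in doing so. A site working from Section 11.1.1 would scan at week 9.

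The difference matters for the comparison because tolerance may differ by arm. Every reason to hold pembrolizumab in the control arm also exists in the combination arm. The combination arm adds the anetumab ravtansine holds in Section 6.2, the rule in Section 6.4 that holds both agents when attribution is unclear, and an eye examination before each later infusion (calendar footnote b). If more cycles slip there and scans slip with them, progression is recorded later in that arm without any drug effect. Section 13.5.3 plans no analysis that allows for scan timing.

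**Working it through.** **1. The plan's own interval.** 3 cycles × 21 days ÷ 7 = 9.0 weeks, the figure in Section 11.1.1. The calendar columns also put the end of cycle 3 at week 9. The schedules are therefore identical when no cycle is late.

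**2. When they separate.** On the calendar reading, a delay of d weeks in any of the three cycles moves the scan to 9 + d weeks. With d = 3 the interval is 12 weeks. With one delay at the 12-week limit it is 9 + 12 = 21 weeks. On the Section 11.1.1 reading it stays at 9.

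**3. Effect on the PFS test if scans follow cycles.** Inputs from the protocol: 49 patients per arm (Section 13.1.3.3) and a median PFS of 6.2 months in both arms (the earlier phase 2 pembrolizumab trial described in Section 2.2.2), which is 6.2 × 52.18 ÷ 12 = 27.0 weeks.

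Assumptions:
- exponential PFS with a true hazard ratio of 1;
- 10% of events are deaths dated exactly, and other events are dated at the next scan;
- follow-up uniform over 18 to 152 weeks;
- control scans exactly every 9 weeks, with slippage in the combination arm only;
- one-sided log-rank test at 0.10 or 0.025.

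Results from 12,000 replicates:

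| Slip in combination arm | Error at 0.10 | Error at 0.025 | Apparent median gain (weeks) |
|---|---|---|---|
| None | 10.6% | 2.9% | 0.0 |
| 3 weeks, 25% of intervals | 10.4% | 2.6% | 0.5 |
| 3 weeks, 50% of intervals | 11.8% | 3.1% | 0.9 |
| 6 weeks, 50% of intervals | 12.8% | 3.5% | 1.8 |
| 1 week, every interval | 15.2% | 4.3% | 0.4 |
| 3 weeks, every interval | 16.2% | 4.7% | 1.3 |
| 6 weeks, every interval | 22.9% | 7.8% | 2.2 |

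The Monte Carlo standard error at 0.10 is √(0.106 × 0.894 ÷ 12,000) = 0.28 percentage points, or about 0.4 for a difference between two rows. The 25% row therefore shows no inflation. The 50% rows show a small increase.

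**4. Rough check on the gain.** Progression falls on average about halfway through an interval, so lengthening every interval by d weeks delays its date by about d ÷ 2. Applied to the 90% of events that are progressions, this gives 0.9 × d ÷ 2 = 0.45, 1.35 and 2.7 weeks for d = 1, 3 and 6. The simulated median gains are 0.4, 1.3 and 2.2.

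**5. A second slip pattern.** Here a fixed share of combination patients slips at each assessment (4,000 replicates, standard error about 0.5 points). Error at 0.10 is 9.1% with no slip, 9.8% (30% of patients, 3 weeks), 12.0% (50%, 3 weeks), 12.3% (30%, 6 weeks) and 13.8% (50%, 6 weeks). The direction is the same and the size similar.

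**6. Reading the last three rows of the table.** The model has no visit window. A uniform slip therefore places every combination scan after the matching control scan, which is why 1 week in every interval does more than 3 weeks in half of them. These rows are an upper end.

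**The case against.** The case on the other side is substantial. The schedules agree as planned. The line in Section 5.5 would do nothing if scans waited for dosing, so the natural reading of the protocol as a whole is calendar time.

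An anetumab ravtansine hold need not move the cycle, because Section 6.4 lets pembrolizumab go on when attribution is clear. The corneal toxicity table in Section 6.2 works by continuing, reducing or stopping anetumab ravtansine, and none of its rows holds a cycle. The one-sided 0.10 level belongs to the response-rate test, not to PFS. The go/no-go rule in Section 13.1.3.3 rests on response rate alone.

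All of this stands, and it limits the size of the problem. It does not remove the ambiguity. Section 5.5 names neither schedule and is placed under the longest interruptions only. Section 6.2 does hold anetumab ravtansine for Grade 3 non-hematologic and for Grade 3 or 4 neutrophil and platelet events, and Section 6.4 holds both agents when the cause is unclear.

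A reader might infer that delays in the combination arm will postpone progression there and that the PFS comparison is biased. The documents do not support that. They give no delay rates for either arm and do not show that sites scan by cycle.

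**Conclusion.** The inconsistency is real: two sections give rules for timing scans that part as soon as a cycle is late, and the line meant to cover interruptions does not choose between them. The consequence is conditional. If sites follow the calendar row and delays are more frequent in the combination arm, PFS could be biased towards it.

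For occasional delays the effect is negligible to small: 10.4% to 12.8% against 10.6% with no slip, with an apparent median gain of 0.5 to 1.8 weeks on a median of 27 weeks. It becomes material only if most intervals slip; the figures of 15.2% to 22.9% are for slippage in every interval. These figures rest on assumed delay rates, slippage in one arm only, and a test level that Section 13.5.3 does not state. PFS is a secondary endpoint, and nothing calculated here bears on the response-rate decision. This is a cheap improvement, not a demonstrated bias.

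**What to change.** In the Section 10 calendar, replace the cycle-based text in the tumor measurement row with: *every 9 weeks from start of treatment in both arms, regardless of dose delays or interruptions*. In Section 5.5, have the line on tumor assessments refer to Section 11.1.1. With both arms on this schedule, the simulated error is the no-slip row (10.6% at 0.10, 2.9% at 0.025) and the median difference is about 0 weeks.

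Two limits on the change:

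- Do not count from randomization. PFS runs from start of treatment, and Section 4.4 allows up to 14 days between registration and treatment, so that anchor would create a new mismatch.
- Do not add scans after treatment ends. Section 5.6 provides only telephone or letter contact for vital status at that stage, and extending imaging is a separate decision with its own cost.

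The cost is one calendar sentence and one cross-reference. Patients without delays have the same scans as now. In patients with delays, scan visits may no longer coincide with dosing visits.
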